Correlation and Comparison of the HepQuant® Disease
Severity Index (DSI) With Hepatic Venous Pressure
Gradient (HVPG)

NCT02523196

Protocol Version: August 11, 2015

Protocol #: 15-0520

Project Title: Correlation and comparison of the HepQuant® Disease Severity Index (DSI) with Hepatic Venous Pressure Gradient (HVPG)

Principal Investigator: [name].

Version Date: August 11th, 2015

I. Hypotheses and Specific Aims:

Hypothesis

The HepQuant® (HQ)-SHUNT test is an appropriate alternative to Hepatic Venous Pressure Gradient (HVPG) testing.

Specific Aims

HQ-SHUNT is safe, simple to administer, noninvasive, cost-effective, and well tolerated by patients. In order to prove that the HQ-SHUNT test is an appropriate alternative to measurement of HVPG we will conduct a head-to-head comparison of HQ-SHUNT to HVPG. In this study, 100 consecutive patients with various etiologies of liver disease who have undergone technically successful HVPG testing will subsequently undergo HQ-SHUNT testing.

Primary Aim 1: Create the ROC curve of the Disease Severity Index (DSI) from HQ-SHUNT for defining patients with (HVPG ≥ 6 mmHg) and without (HVPG < 6 mmHg) portal hypertension. From the ROC, define the optimal cutoff of DSI and the sensitivity, specificity, and positive and negative predictive values.

Primary Aim 2: In patients with portal hypertension (HVPG ≥ 6 mmHg), define the optimal relationship of DSI to HVPG.

Exploratory Aims

Approximately 90% of patients undergoing HVPG will have liver biopsy performed as part of the procedure. In addition, most of the patients undergoing HVPG will have undergone or will undergo upper gastrointestinal endoscopy (EGD) to evaluate for varices and variceal treatment. This allows a head-to-head comparison of DSI from HQ-SHUNT with HVPG in identifying patients with cirrhosis and patients with varices. Finally, we will also compare the tolerability of both HVPG and HQ-SHUNT, since tolerability of procedures is critical for patient acceptance and the ability to perform serial testing.

Exploratory Aim 1: Compare the cutoffs of DSI 16.5 and HVPG 6 mmHg in identifying patients with cirrhosis.

Exploratory Aim 2: Compare the cutoffs of DSI 20 and HVPG 10 mm Hg in identifying patients with varices.

Exploratory Aim 3: Survey patients on their experience of having both HQ-SHUNT and HVPG procedures.

II. Background and Significance:

The Clinical Problem in Liver Disease Assessment and Liver Disease Drug Development

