Both HVPG and HQ-SHUNT results correlate with fibrosis stage, prevalence of cirrhosis, and the prevalence and size of varices [7], [8], [9]. DSI appears to have a better and more linear correlation with fibrosis, and more sensitivity at lower fibrosis stages than HVPG (Fig. 3). However all the results summarized above were from separate studies and the two methods have never before been compared in a head-to-head fashion.

IV. Research Methods

A. Outcome Measure(s):

The following outcome measures will be assessed for each Specific Aim:

Primary Aim 1. Two measurements will be compared, HVPG and DSI. The HVPG test results will define the patients with portal hypertension (HVPG ≥ 6 mmHg). DSI will be determined from the HepQuant (HQ)-SHUNT test and the DSI cutoff for portal hypertension will be defined from ROC analysis.

Primary Aim 2. Two measurements will be compared, HVPG and DSI. The relationship between these measurements, in the patients with portal hypertension, will be analyzed by linear and nonlinear regression.

Exploratory Aims:

Exploratory Aim 1. The outcome measure is cirrhotic fibrosis score on liver biopsy. Prevalence of cirrhosis will be determined for cutoffs of DSI 20 and HVPG 6 mmHg.

Exploratory Aim 2. The outcome measure is medium to large varices at EGD. Prevalence of varices will be determined for cutoffs of DSI 20 and HVPG 10 mmHg.

Exploratory Aim 3. The outcome measure is patient tolerability for testing procedures defined by the Patient Survey.

B. Description of Population to be Enrolled:

Inclusion Criteria

- Liver disease patient scheduled to have an Hepatic Venous Pressure Gradient (HVPG) procedure
- At time of enrollment, being between the ages of 18 and 75

Exclusion Criteria

- Concomitant treatment with both a beta blocker and an ACE inhibitor
- Concurrent hepatic malignancy. Patients with a history of treated HCC can be included if there is no evidence of recurrent disease at the time of this study.
- Unstable angina or history of myocardial infarction or congestive heart failure within 6 months prior to enrollment into this study
- Renal insufficiency with chronic kidney disease stage 4 or 5 (GFR < 30 mL/min/1.73m²)
- Crohn's disease or any active intestinal inflammatory condition
- Having had an ileal resection
- Diabetic Gastroparesis
- Pregnancy or intent to become pregnant. Urine pregnancy tests will be performed prior to HQ SHUNT testing.
- Inability to consent for one's self

Stopping Criteria

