Correlation (R) is the assumed sample correlation.
Width if R = 0.0 is the maximum width for a confidence interval with sample size N.

For the linear regression analysis, a sample size of 50 achieves 80% power to detect a change in slope from 0 under the null hypothesis to 0.50 under the alternative hypothesis when the standard deviation of DSI is 3, the standard deviation of HVPG is 4.00, and the two-sided significance level is 0.05.

General Statistical Analysis

Primary Aim 1. It is expected that both HQ-SHUNT results and HVPG measurements will reflect the extent of liver disease. Higher pressures will in general be associated with lower Systemic HFR and Portal HFR, and with higher SHUNT and DSI. The performance of DSI to identify patients with portal hypertension (HVPG ≥ 6 mmHg) will be determined by ROC analysis. Optimal DSI cutoff, sensitivity, specificity, PPV, and NPV will be defined.

Primary Aim 2. We will develop models of the relationships of HQ-SHUNT test results to the HVPG test results based on correlations. We expect there to be a linear relationship for HVPG pressures between 6 and 25 mmHg (i.e. in patients with portal hypertension) and will assess the correlation (with 95% confidence intervals) for HVPG vs. DSI in the 50 patients expected to have HVPG pressures ≥ 6 mmHg. Linear regression will be used to assess the relationship between these variables, taking other covariates into account, and R^2 values will be reported.

Exploratory Aims:

Exploratory Aim 1. It is expected that both HQ-SHUNT results and HVPG measurements will, in general, reflect the extent of liver disease, as measured by the liver fibrosis stage and by the D'Amico cirrhosis stage. Regression models will be developed of the relationships of HQ-SHUNT test results to fibrosis stage and to cirrhosis stage. Likewise regression models will be developed of the relationship of HVPG portal pressure to fibrosis stage and to cirrhosis stage. It is expected that correlations will be found similar to those shown in Fig 3, but now demonstrated in the same patient population.

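### Exploratory Aim 1 gives two DSI cutoffs for cirrhosis (16.5 and 20) against the same HVPG 6 mmHg comparator, and the analysis plan names neither

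*Combined protocol and SAP*

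**What the plan says.** Three places in the combined protocol and SAP deal with Exploratory Aim 1.

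- **Section I, Exploratory Aims:** "Compare the cutoffs of DSI 16.5 and HVPG 6 mmHg in identifying patients with cirrhosis".
- **Section IV.A, Outcome Measure(s):** the outcome is a cirrhotic fibrosis score on biopsy, and "Prevalence of cirrhosis will be determined for cutoffs of DSI 20 and HVPG 6 mmHg".
- **Section IV.F, General Statistical Analysis:** "Regression models will be developed of the relationships of HQ-SHUNT test results to fibrosis stage and to cirrhosis stage", and "Likewise regression models will be developed of the relationship of HVPG portal pressure to fibrosis stage and to cirrhosis stage". No DSI cutoff, HVPG cutoff or comparison of cutoffs appears under this aim.

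The neighbouring aim does not have this problem. Section I states "Exploratory Aim 2: Compare the cutoffs of DSI 20 and HVPG 10 mm Hg in identifying patients with varices", and Section IV.A repeats the same pair of values.

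**The concern.** The aim, the target condition and the HVPG comparator are the same in Sections I and IV.A, but the DSI threshold is not. Each section gives a single value and neither refers to the other, so they cannot be read as a main and a secondary analysis.

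The threshold decides who counts as test-positive. Raising it from 16.5 to 20 can only remove positives, so sensitivity at 20 cannot exceed sensitivity at 16.5, and specificity at 20 cannot be lower. The prevalence of cirrhosis among patients above the cutoff, which is the measure in Section IV.A, can change as well. HVPG 6 mmHg stays fixed, so the comparison between the two tests may depend on which section is followed. With both numbers in the protocol, either could be reported afterwards as the planned one.

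**Working it through.** **Is the conflict real?**

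| Place | DSI cutoff for cirrhosis | HVPG comparator |
|---|---|---|
| Section I, Exploratory Aim 1 | 16.5 | 6 mmHg |
| Section IV.A, Exploratory Aim 1 | 20 | 6 mmHg |
| Section IV.F, Exploratory Aim 1 | none | none |

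There is one protocol version (August 11, 2015) and no amendment log, so neither value is superseded text. Both sentences are complete, with no redaction or broken table. The value 16.5 appears nowhere else. Elsewhere the value 20 is used only in connection with varices: Section I and Section IV.A under Exploratory Aim 2, the Background, and Section IV.G. No passage reconciles the two.

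**How many patients could be affected?** The plan gives no power or precision figure for this aim, so there is nothing of its own to reproduce. The following is for scale only.

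Inputs:

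- Cutoffs 16.5 and 20, from Sections I and IV.A. The gap is 20 − 16.5 = 3.5 DSI units.
- SD of DSI = 3, from the Primary Aim 2 power statement in Section IV.F ("when the standard deviation of DSI is 3"). It is given there for the regression in patients with portal hypertension, not for biopsied patients.
- SD 5 and SD 7, the mean DSI and normality are assumptions.
- Biopsied patients: "Approximately 90% of patients undergoing HVPG will have liver biopsy performed as part of the procedure" (Section I). Taking the 100 patients of Section I, 0.90 × 100 = 90.

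Formula, with mean m, standard deviation s and Φ the standard normal distribution function:

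P(16.5 < DSI < 20) = Φ((20 − m)/s) − Φ((16.5 − m)/s)

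Two worked cases with s = 3:

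- m = 14: Φ(2.000) − Φ(0.833) = 0.97725 − 0.79766 = 0.180.
- m = 18.25, the midpoint of the interval, where the share is largest: 2 × Φ(0.5833) − 1 = 2 × 0.72016 − 1 = 0.440.

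| Mean DSI | SD 3 | SD 5 | SD 7 |
|---|---|---|---|
| 10 | 0.015 | 0.074 | 0.100 |
| 14 | 0.180 | 0.193 | 0.165 |
| 18.25 | 0.440 | 0.274 | 0.197 |
| 22 | 0.219 | 0.209 | 0.172 |
| 30 | 0.000 | 0.019 | 0.050 |

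For means of 14 to 22, multiplying the unrounded shares by 90 gives 16.2 to 39.6 patients (SD 3), 17.4 to 24.6 (SD 5) and 14.8 to 17.8 (SD 7).

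These are shares of patients whose classification changes. They are not differences in sensitivity or specificity, which also depend on how many of those patients have cirrhosis.

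**The case against.** The strongest case on the other side accepts the contradiction and disputes its weight.

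- **The aim is exploratory.** It has no power, alpha or decision rule, and the only analysis written for it, the regression in Section IV.F, uses no cutoff. DSI is continuous, so both cutoffs could simply be reported. This is true, and it limits the severity. It does not remove the conflict: Sections I and IV.A both promise a cutoff-based result, and they promise different ones.
- **The value 20 may be a slip.** It is otherwise tied to varices and stands in the next line of Section IV.A. A carry-over is plausible, but the documents do not show it, so the sponsor has to confirm the value.
- **The larger shares are optimistic about spread.** The 44% needs SD 3 in all biopsied patients and a mean at the exact midpoint. Section IV.G reports mean DSI of 14, 20 and 35 in PSC patients with no varices, varices and decompensation. If, as an assumption, these groups were equally common, the mean would be 23 and the between-group SD alone 8.8. A normal distribution with those values puts about 14% between the cutoffs. A mixture of the three groups with within-group SD 3 gives (0.180 + 0.378 + 0.000)/3 = 0.186, about 19%. This point stands: the upper figures should not lead. A share of 14% to 19% is still not negligible.
- **The count of 90 is an expectation.** Biopsy is not required for enrolment (Section IV.D), and Section IV.C enrols 110 rather than 100. This also stands, so the patient numbers are approximate.
- **The missing cutoff comparison in Section IV.F is a separate gap.** It would remain if the two values agreed. It matters here because the analysis plan is where the conflict could have been settled.

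**Conclusion.** The concern holds. Exploratory Aim 1 has two different prespecified DSI cutoffs for cirrhosis against one HVPG comparator, and the analysis plan does not choose between them. The documents do not establish which was intended.

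That conclusion rests on the text alone and on no distributional assumption. Only the size does. Under normality, with a mean DSI near the cutoffs and SDs from 3 to 7, roughly one in six to just over two in five biopsied patients would change classification. With a wider spread the share is nearer the low end, and with a mean as far away as 10 or 30 it is 10% or less. The two cutoffs give identical results only if no biopsied patient falls between them.

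This should be fixed, but it does not threaten the trial: the primary aims and the sample size are unaffected.

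**What to change.** Before any analysis:

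1. The sponsor confirms one DSI cutoff for cirrhosis and states it identically in Section I and Section IV.A.
2. Section IV.F, Exploratory Aim 1, gains a sentence describing the comparison of that cutoff with HVPG 6 mmHg and naming the measure compared (for example sensitivity and specificity, or prevalence of cirrhosis above the cutoff).
3. If both values are wanted, one is named as the main comparison and the other as a sensitivity analysis.

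The cost is a one-line correction and one added sentence. No extra data are needed, because DSI is calculated as a continuous score (Section IV.C) and any cutoff can be applied to it.

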HQ-SHUNT, invented at CU by [name], MD, fulfills an unmet need in liver drug development and in clinical trials of liver disease – a noninvasive, accurate, safe, easy-to-administer, and cost-effective liver function test [1]. In this study we will define the relationships of the Disease Severity Index (DSI) and other parameters from the HQ-SHUNT test to HVPG.

[figure not shown]
[figure not shown]
Hepatic Venous Pressure Gradient (HVPG) has been used in clinic trials, research studies, and clinical medicine to quantify liver disease severity and progression. HVPG > 6 mmHg signifies portal hypertension and HVPG > 10 mmHg increases risk for ascites and variceal hemorrhage. Portal hypertension is a consequence of advanced liver disease and HVPG quantifies risk for clinical outcomes. Measuring HVPG is technically challenging, requires specialized radiologic expertise and equipment, not embraced by patients, and is risky and expensive. Despite the latter concerns, the FDA accepts HVPG as an endpoint in clinical trials of treatments for chronic liver disease. A noninvasive accurate alternative to HVPG is needed.

The HQ-SHUNT test is not FDA approved but over 1000 tests have been done in over 500 subjects or patients without any safety concerns. Outputs from the HQ-SHUNT test include clearances of intravenous (Systemic Hepatic Filtration Rate (HFR)) and oral (Portal HFR) cholate, SHUNT (ratio of Systemic HFR to Portal HFR), and Disease Severity Index (DSI). Healthy controls have DSI <10; DSI >20 is associated with risk for cirrhosis with varices. DSI outperformed liver biopsy and standard laboratory tests in predicting risk for future clinical outcomes. Like HVPG, DSI from HQ-SHUNT is heavily weighted to measure changes in the portal circulation – but, compared to HVPG, HQ-SHUNT is safe, noninvasive, simple to administer, well tolerated by patients, requires no specialized expertise or equipment, and is relatively inexpensive. HQ-SHUNT and DSI may be the noninvasive accurate alternative to HVPG.

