- Decision by subject to withdraw from study for any reason
- Development of any of the above-mentioned exclusion criteria (being diagnosed with a hepatic malignancy, becoming or intending to become pregnant, clinical decompensation, development of unstable coronary disease, congestive heart failure or renal insufficiency with GFR < 30mL/min/1.73m²)
- Adverse reaction to test compounds

C. Study Design and Research Methods

Patient Selection

The HVPG procedure costs ~\$8500 and is currently ordered on a case-by-case basis as part of the standard of care (SOC) for liver disease. Patients already scheduled to have an HVPG measurement will be recruited to participate in this study of "Correlation and Comparison of HQ-SHUNT with HVPG". The HVPG procedure is quite uncomfortable, requires sedation and commitment of an entire day. Therefore, patients will not undergo HQ-SHUNT testing on the day of their HVPG, but rather within a window of ±60 days of their HVPG. Liver disease progresses slowly over years so that HQ-SHUNT® and HVPG results will represent the patient's current status. Patients will be censored in the analysis if clinical decompensation occurs between the HQ-SHUNT and HVPG tests.

We will enroll 110 patients into the study. Over 90% of all HVPG tests performed by UCH Radiology are ordered through the Hepatology clinic at UCH. Patients and care providers in the Hepatology clinic will be made aware of the "Correlation and Comparison of HQ-SHUNT with HVPG" study via direct communications. Patients may be enrolled within 60days following the performance of the HVPG procedure. HQ-SHUNT tests will only be performed in the patients who had a technically successful HVPG test as determined by the radiologist performing the procedure. All HQ-SHUNT tests will be performed within the 60 days following the HVPG test. HQ-SHUNT will only be performed in patients whose clinical status is stable and who have not had any major intervening procedures such TIPS or surgical shunt. Elective EGD and banding of varices, in an otherwise clinically stable patient is an allowable intervention.

PROCEDURES AND METHODS

HVPG

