
the d4-Cholate dose / d4-Cholate AUC and the Portal HFR is the Oral Clearance normalized to patient weight (mL/min/kg). The concentration of d4-Cholate (μM) at 60 min was found in previous studies to exhibit a reasonable correlation ($r^2 = 0.88$) with Portal HFR so this single blood sample will also be evaluated as a simplified testing approach. The cholate shunt fraction is calculated as $100\% \times \text{Systemic HFR} / \text{Portal HFR}$. The DSI is calculated as $5.34 (\text{SHUNT}) - 6.65 (\text{Lne Portal HFR}) - 8.57 (\text{Lne Systemic HFR}) + 44.66$, and varies from ~ 0 in the healthiest liver to ~ 50 at liver failure.

SURVEY OF PATIENT TOLERABILITY

After undergoing both procedures, at the completion of the HQ-SHUNT test (always the last test), the patients would then be given two surveys, one for HVPG and another for HQ-SHUNT. The purpose of these surveys is to have the patient record their experiences with each procedure as regards their pain, discomfort, inconvenience, and willingness to undergo the procedures again. The two surveys are very similar but are nuanced for the type of testing.

D. Description, Risks and Justification of Procedures and Data Collection Tools:

Only patients who are already scheduled to have an HVPG procedure as part of their standard-of-care will be recruited to participate in this study. Most of these patients will also have liver biopsy either prior to or at the time of the HVPG procedure. In addition, these patients often undergo esophageal endoscopy procedures as part of their standard-of-care. While we will collect the data from these procedures, the subjects will not be exposed to any additional risks from these procedures beyond those associated with these standard-of-care procedures. Neither biopsy nor EGD are requirements for enrollment into this study of HVPG and HQ-SHUNT. The only additional risks will be those incurred from the HQ-SHUNT test.

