Exploratory Aim 2. HQ-SHUNT test results will be compared to HVPG test results at identifying patients with all sizes of varices, as well as at identifying just those patients with medium to large varices that require therapeutic intervention, usually banding. These comparisons will be made using ROC curves and their associated c-statistics. The optimum diagnostic cutoffs of each test will be determined from the ROC curves by the Youden index (J statistic). The sensitivity, specificity, PPV, and NPV of each test will be compared at their respective optimum diagnostic cutoffs.

Exploratory Aim 3. For each procedure, HVPG and HQ-SHUNT testing, the patients will report their pain, discomfort, inconvenience, overall experience, and willingness to undergo repeat testing, each on a scale of 1 to 10. The numerical scores of each question will be compared between the HVPG and HQ-SHUNT testing, in terms of mean score, standard deviation, and statistical significance (t-test).

G. Summarize Knowledge to be Gained:

Overall this study will demonstrate whether The HQ-SHUNT test results can generate physiological information on liver disease patients that is as good, or better, than HPVG pressure measurements. A close correlation between HQ-SHUNT test results and HPVG pressure measurements would allow the safer, less invasive, lower cost HQ-SHUNT test to replace HVPG in patient assessment and in clinical trials of new liver disease therapies and therapeutic agents. However the HQ-SHUNT test reports on the systemic clearance, portal clearance, and portal-systemic shunt and provides a more comprehensive picture of the portal circulation than just the portal pressure. For example, the presence of extensive or large collaterals, such as a spleno-renal collateral, should relieve portal pressure, reduce varices, and reduce the HVPG; while, in contrast, HQ-SHUNT would reveal an increase in SHUNT and DSI. In terms of disease severity, HVPG would be falsely low, while HQ-SHUNT would report accurately.

Varices are clinically very serious because they require intervention to prevent internal bleeding. An HVPG > 10 mm HG has been associated with a risk of varices. A DSI > 20 similarly indicates a risk of large varices, ROC c-statistic 0.82, sensitivity 86%, specificity 65%. This study allows a direct comparison in the same patients of the relative ability of HQ-SHUNT and HVPG to identify patients with varices.

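### Exploratory Aim 2 compares DSI and HVPG for varices only where EGD happened to be done; the plan neither reports nor adjusts for that selection, which could affect the two tests differently if EGD depends on HVPG.

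*Combined protocol and SAP*

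**What the plan says.** The outcome measure for Exploratory Aim 2 (section IV.A) is varices of at least medium size on EGD, with cutoffs of DSI 20 and HVPG 10 mmHg. Section I gives the same two cutoffs. Section IV.F adds ROC curves, c-statistics and Youden cutoffs, for varices of any size as well as the larger ones: "The sensitivity, specificity, PPV, and NPV of each test will be compared at their respective optimum diagnostic cutoffs".

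The reference standard is not guaranteed. Section IV.D states that "Neither biopsy nor EGD are requirements for enrollment into this study of HVPG and HQ-SHUNT" and that "these patients often undergo esophageal endoscopy procedures as part of their standard-of-care". Section I expects that "most of the patients undergoing HVPG will have undergone or will undergo upper gastrointestinal endoscopy (EGD) to evaluate for varices". No number is given, and EGD may come before or after HVPG.

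HVPG is a clinical test, "currently ordered on a case-by-case basis as part of the standard of care (SOC) for liver disease" (section IV.C). HQ-SHUNT is investigational: "The HQ-SHUNT test is not FDA approved but over 1000 tests have been done" (section II). On timing, section IV.C says "All HQ-SHUNT tests will be performed within the 60 days following the HVPG test". The same section also gives a window of 60 days on either side of HVPG, and the two statements must be reconciled.

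The plan does not say how patients without EGD are handled, sets no time window for EGD, and does not say whether the clinician deciding on EGD sees HVPG or DSI. It has no comparison of patients with and without EGD and no sensitivity analysis for missing EGD.

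**The concern.** If a high HVPG makes EGD more likely, patients with EGD over-represent high HVPG values. Among them HVPG's sensitivity is too high and its specificity too low. DSI is affected only through its correlation with HVPG.

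Using the same patients for both tests does not cancel this, because selection acts directly on one test and indirectly on the other. Two tests of equal accuracy could then look different, and on specificity the false difference would favour DSI, the test under study. The protocol itself links HVPG above 10 mmHg to varices (section IV.G) and to variceal bleeding (section II), so it is plausible that HVPG influences EGD.

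**Working it through.** **Plan's own figure.** None exists for this aim. The nearest is the 80% power for Primary Aim 1 (AUC 0.65 vs 0.7945, 50 + 50 patients). It reproduces at 79.5% with the Hanley-McNeil variance, but it does not bear on this point.

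**Assumptions, none from the documents.** Both tests have true sensitivity (Se) 0.80 and specificity (Sp) 0.65, and prevalence is 40%. EGD depends only on HVPG, with rate v1 at HVPG ≥ 10 and v0 below, and all EGDs follow HVPG. For DSI, a binormal model is used with within-disease correlation 0 to 0.5 between the tests.

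**Expected counts per 100 patients**
- HVPG ≥ 10: 0.80 × 40 = 32 with varices and 0.35 × 60 = 21 without.
- HVPG < 10: 8 with varices and 39 without.

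**HVPG at the fixed cutoff, complete cases**

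Apparent sensitivity = Se·v1 / (Se·v1 + (1 − Se)·v0); apparent specificity = Sp·v0 / (Sp·v0 + (1 − Sp)·v1).

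- 90% vs 50%: 28.8/(28.8 + 4.0) = 0.878; 19.5/(19.5 + 18.9) = 0.508. Patients without EGD: 100 − 71.2 = 28.8.
- 95% vs 70%: 30.4/(30.4 + 5.6) = 0.844; 27.3/(27.3 + 19.95) = 0.578.
- 90% vs 80%: 28.8/(28.8 + 6.4) = 0.818; 31.2/(31.2 + 18.9) = 0.623.

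**DSI at its fixed cutoff (simulation, 2,000,000 patients)**

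| EGD rates | HVPG Se/Sp | DSI Se/Sp | Specificity gap |
|---|---|---|---|
| 90% vs 50% | 0.88/0.51 | 0.80–0.82/0.60–0.65 | 10–14 points |
| 95% vs 70% | 0.84/0.58 | 0.80–0.81/0.63–0.65 | 5–7 points |
| 90% vs 80% | 0.82/0.62 | 0.80–0.81/0.64–0.65 | 2–3 points |

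If half of the EGDs are chosen independently of HVPG, the first two gaps fall to about 5–7 and 2–4 points. If all are, they are zero.

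**Predictive values at the fixed cutoffs.** HVPG's PPV is unbiased: v1 cancels, leaving 32/53 = 0.604. DSI's is not. At correlation 0 and 90% vs 50%, the EGD rate is 0.80 × 0.9 + 0.20 × 0.5 = 0.82 with varices and 0.35 × 0.9 + 0.65 × 0.5 = 0.64 without. DSI's apparent PPV is then 0.80 × 32.8/(0.80 × 32.8 + 0.35 × 38.4) = 26.24/39.68 = 0.661, about 6 points too high. At 95% vs 70% the two rates are 0.90 and 0.7875, and the PPV is 28.8/(28.8 + 16.54) = 0.635, about 3 points too high. Over correlations 0 to 0.5 the two scenarios together give about 2 to 6 points.

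**Youden cutoffs and c-statistics (section IV.F).** In the same simulations the specificity gap is about 3 points or less, and it can reverse in the milder scenarios. The true c-statistic is 0.807; at 90% vs 50%, HVPG gives about 0.795 and DSI 0.800–0.808.

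**Second set of inputs.** Section IV.G quotes 86% sensitivity and 65% specificity for DSI > 20. Taking these for both tests, with an assumed prevalence of 30% and EGD rates of 95% vs 50%, HVPG appears as 0.92/0.49 and DSI as 0.86–0.88/0.59–0.65 (correlation 0 to 0.6). The pattern is the same.

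**Does correction work?** Begg-Greenes at 90% vs 50%: the varices rate among those with EGD is 28.8/47.7 = 0.604 at HVPG ≥ 10 and 4.0/23.5 = 0.170 below. Applied to all 53 and 47 patients, this returns 32 and 8 cases, so sensitivity is 32/40 = 0.80 and specificity 39/60 = 0.65. Inverse-probability weighting restores 0.80/0.65 for DSI as well. Both succeed because the illustration makes EGD depend on HVPG alone.

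**The case against.** **The premises are not facts in the plan.** A reader might infer that EGD is decided by clinicians who know HVPG but not DSI. The documents do not support that as a general statement. Section I allows EGD to precede HVPG, and such an EGD cannot have been prompted by the HVPG result. No section says that DSI is withheld, or that a high HVPG triggers EGD. That DSI plays little part in the decision is a reasonable inference from its investigational status and from HQ-SHUNT being the last test (section IV.C), but no more. This objection stands, and it makes the bias conditional.

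**The larger figures belong to the fixed cutoffs.** Section IV.F plans sensitivity and specificity at Youden cutoffs, where the distortion is small. This also stands. Fixed cutoffs are, however, named for this aim in sections I and IV.A.

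**Section IV.A speaks of prevalence by cutoff, which is a predictive value, and HVPG's is unbiased under the assumed selection.** That is correct for HVPG. It does not rescue the comparison, because DSI's PPV is still inflated.

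**A correction may not remove the bias.** EGD is done "will have undergone or will undergo upper gastrointestinal endoscopy (EGD) to evaluate for varices and variceal treatment", so some patients may have EGD because varices are already known. That is selection on the outcome, which weighting on HVPG, DSI and laboratory values does not remove. Laboratory values from the HQ-SHUNT day may also postdate the EGD decision. A reader might conclude that the analysis requires a correction that would put it right; the documents support only a sensitivity analysis.

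**Importance.** The aim is exploratory. At 90% vs 50% about 38 patients without varices have EGD, so the standard error of HVPG's specificity is √(0.508 × 0.492/38.4) = 0.08. Gaps of 2 to 3 points are well inside sampling error.

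**Conclusion.** The concern holds in conditional form. EGD is optional and clinically driven, the plan is silent on patients without it, and where EGD followed a known HVPG the missing results may bias the two tests differently. The direction and the 5 to 14 points at fixed cutoffs rest on assumed EGD rates, on all EGDs following HVPG, and on equal true accuracy of 0.80/0.65. The real size cannot be computed, because the documents give no EGD rates by HVPG level. The documents do not establish that the comparison is biased, or that any advantage seen for DSI would be an artefact. No primary aim is affected. This is a low-cost improvement to an exploratory analysis.

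**What to change.** In Exploratory Aim 2 (sections IV.A and IV.F):

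1. Record the EGD date relative to HVPG and HQ-SHUNT.
2. Tabulate patients with and without EGD by HVPG < 10 and ≥ 10 mmHg and by DSI < 20 and ≥ 20. This shows whether the problem exists.
3. Keep the complete-case result, and report beside it a Begg-Greenes or inverse-probability-weighted sensitivity analysis for both tests, using HVPG, DSI and recorded laboratory values.
4. State the assumption that EGD depends only on recorded variables, and that selection on already known varices is not removed.

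The cost is one recorded date, one table and one added analysis, with no extra EGD. With about 100 patients the weighted intervals will be wider than the complete-case ones.
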